7.4 Unblinding

Unblinding is not applicable as PIs, RNs and pharmacists will be aware of treatment allocation. Participants will not be blinded to the treatment allocation either, as there is no placebo and both treatments are given at different frequencies (daily vs weekly).

The blinded assessor who carries out the severity assessment will be blinded to the trial allocation.

7.5 Accountability Procedures for Study Treatments

All IMP is to be sourced via usual NHS procurement arrangements. The research team will liaise with the local pharmacy department to ensure that the site has enough of the IMP in stock with appropriate shelf life to be used in the study.

Responsible site personnel must maintain accurate accountability records of the IMP dispensed, including details of the manufacturer, name, form, strength, batch number, expiry date and quantity, to whom dispensed and date of transaction. Local procedures should be used if the manufacturer issues a recall.

7.6 Assessment of Compliance with Study Treatment/s

Patients should be instructed to return any unused IMPs.

Accountability Log provides space to record IMP supplies returned by trial patients before destruction. Returned or unused IMP doses should be disposed/destroyed on an ongoing basis according to local policy.

7.7 Concomitant Medications/Treatments

A concomitant medication/treatment is any drug or substance administered between the screening visit and the visit at week 60. All such medications should be reported to the investigator and recorded on the Concomitant Medications CRF.

7.7.1 Medications Permitted

It is expected that all trial participants will be on concomitant topical therapy for their atopic eczema, in particular regular emollients but also (antiseptic) bath additives and mild-topotent topical corticosteroids (TCS) of the patient's/local investigator's choice. Topical calcineurin inhibitors and oral antihistamines and antibiotics as well as rescue oral corticosteroids are also permitted.

Any medication required for any ongoing illness (illnesses not listed in the exclusion criteria in section 5.2), birth contraception and any rescue medications will also be permitted and recorded both during the treatment and follow up period.

The following are also permitted medications:

- Oral contraceptives or hormone-replacement therapy (also refer to section 7.7.2 for potential drug interactions)
- Maintenance therapy for other medical conditions listed in the patients' medical history at the time of screening
- Medications for the treatment of asthma which may include but are not limited to inhaled therapies, such as corticosteroids, short acting bronchodilators, combination corticosteroids/long acting bronchodilators, and oral therapies (eg montelukast, theophylline)
- Intranasal corticosteroids used for the treatment of allergic rhinitis
- Medications such as paracetamol and non-steroidal anti-inflammatory drugs (eg
 ibuprofen) and routinely-taken dietary supplements, including vitamins, are allowed at
 the discretion of the local PI and provided that the medication in question has no
 discernible impact on the study
- Fixed regimen of psychiatric medications, including but not limited to tricyclic antidepressants, serotonin reuptake inhibitors, or benzodiazepines
- Antiviral medications to treat non-systemic Herpes simplex virus (eg acyclovir for cold sores or herpes zoster).
- Inactivated vaccine
- Antibiotics for treatment of atopic eczema-related skin infections, unless specified in the protocol

Female patients who have attained menarche will undergo a pregnancy test at the screening and baseline visit. They will be counselled against pregnancy during the course of treatment, and will be advised to use highly effective contraceptive measures if appropriate. Any pregnancies that do occur during the study must be reported using a pregnancy CRF to the CTRC within 24 hours of the participating site becoming aware.

7.7.2 Medications Not Permitted/ Precautions Required

The local investigator should instruct the patients and their parents/caregivers to notify the study site about any new medications he/she takes after the start of the study drug.

The following therapies are prohibited during the study **for all patients**:

- Use of wet wraps or other occlusive dressings
- Concomitant systemic anti-inflammatory or immunosuppressant medication, including but not limited to azathioprine and mycophenolate mofetil
- Phototherapy or tanning booth/parlour
- Allergen immunotherapy
- Biologic agents
- Live vaccines 4 weeks prior to baseline, while in the study, and for 12 weeks following the last dose of study drug.

Patients who discontinue the study drug due to the use of one of the above should be asked to continue with study assessments.

Patients who use any of the following therapies during the study should not be discontinued from study drug and should not be withdrawn from the study. The investigator must enter the therapies into the concomitant medications CRF. The investigator should contact the trial coordinator (who will contact the Chief Investigator) if questions arise regarding the safety risks associated with continuing study drug.

- Other/alternative therapies which may include, but is not limited, to acupuncture, phytotherapy, and herbal substances used for the treatment of atopic eczema. The investigator should ask the patient to stop these therapies for the remainder of the study if in their opinion it is safe to do so.
- Patients are advised to avoid self-medication with over the counter ibuprofen if on the
 methotrexate arm of the study due to the potential interaction between the two
 medicines. Patients are instead advised to take paracetamol. If accidental use of over
 the counter ibuprofen occurs, this will not lead to the withdrawal of the patient from the
 study drug or trial, and clinicians are advised to monitor closely in line with current
 practice.

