8 ASSESSMENTS AND PROCEDURES

8.1 Schedule for assessments during the treatment and the follow-up phase

The total duration of the study is for 60 weeks (following randomisation). Patients will receive IMP for 36 weeks and followed up for 60 weeks post randomisation. The below interventions will take place according to the study visit schedule table at the stated time points. However, the following visit windows are allowed: 2 days +/- at week 1 and 2, 1 week +/- at week 4, and then 2 weeks +/- thereafter.

Table 9: Schedule of study procedures

		Week 0	Week 1 (MTX arm only)	Week 2	Week 4	Week 8	Week 12	Week 20	Week 28	Week 36	Week 48	Week 60	Unschedule d visit
Procedures	Screening Visit	Baseline/ Randomis ation	Visit 1	Visit 2	Visit 3	Visit 4	Visit 5	Visit 6	Visit 7	Visit 8	Visit 9	Visit 10	
Informed consent	х												
Inclusion/exclusion criteria	х	х											
Medical history	х												
Concomitant drugs	х	х	х	x	x	х	х	х	x	х	х	x	х
Demographics	х												
Physical exam (including mouth/throat examination and chest auscultation)		x	x	x	x	x	x	x	x	x	x	х	
o-SCORAD)	х	х			x	х	x	х	x	х	х	х	x ^h
EASI, IGA		x			x	х	х	x	x	х	х	х	x ^h
POEM (patient assessed) Parent and child QoL		х			х	х	х	х	x	х	х		
(CDLQI/IDQOL & DFI)		х					х			х	х	х	
Child HRQL (CHU-9D)		х					х			х	х	х	
Resource Use (patient diary)		х			x	х	x	х	x	х	х	х	
Height & weight		х	х	х	x	х	х	х	x	х		х	
Height	х												() '(
Blood pressure		х		х	x	х	х	х	x	х		х	x (only if required)
Adverse events (AE & SAE)			x	x	х	х	х	х	x	х			x
Safety bloods ^b	Х ^с		х	x	x c	х	х	х	x	х		x	x (only if required)
Chest X-Ray d	х												
Pregnancy test (beta-HCG) Confirmation of appropriate	х	х											
contraception use, where applicable	x	x	x	x	x	x	x	x	x	x	x	x	x
Urine sample collection (NAG)		х		x			x			х		х	
Randomisation		x											
Study drug dispensing (as needed at each visit)		х			x	х	х	х	x				
MTX metabolite level (blood)				x		х	x			х			
CyA trough level (blood) e				х		х	х			х			_
Cystatin C level (blood)		x		х		х	х			х		х	
Creatinine level (blood)		х		x		х	х			х		х	
Tape stripping for cutaneous metabolic work f		х					х			х		х	
Collection of blood for mechanistic studies ^g		х					x			х		х	
Collection of blood/saliva for FLG genotyping i		х											

8.1.1 Assessments:

- a. Children will be assessed by trained blinded assessors at 0, 4, 8, 12, 20, 28, 36, 48 and 60 weeks (o-SCORAD, EASI, & IGA). POEM (included in the patient diary) will be completed by the patient/parent at home.

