8.2 Procedures for Assessing Efficacy

Efficacy of trial treatments will be assessed throughout the period of the study using objective measures.

The first co-primary outcome measure for the trial is change in atopic eczema severity between baseline and 12 weeks of treatment, using the objective SCORing Atopic Dermatitis (o-SCORAD) severity index, conducted by the blinded assessor (independent member of the research team) at baseline and at 12 weeks.

The second co-primary outcome is the time to the first significant flare after treatment cessation in the MTX vs CyA groups. The total number of flares will also be recorded in questionnaires. The time to the first significant flare is defined as the (earliest) time that a patient either re-started systemic treatment or returns to their baseline o-SCORAD (or worse), following cessation of trial treatment*.

The secondary outcome of change in atopic eczema severity using the o-SCORAD, EASI, IGA and Patient Oriented Eczema Measure (POEM) scores will be assessed between baseline and 12, 36, 48, 60 weeks.

* This refinement to the definition of the co-primary outcome was made, as it was felt that many patients may not ever return to their baseline (or worse) o-SCORAD following treatment cessation but still require systemic therapy because of the severity of their disease and/or the impact this has on their quality of life. The original wording of the definition did not fully reflect real world practice and treatment of a significant disease re-flare after systemic treatment cessation. The TMG consequently proposed the suggested refinement of the definition which was subsequently agreed by the independent oversight committees of the trial, the IDSMC and TSC. Those involved in the decision making were blind to all study results.

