11 ETHICAL CONSIDERATIONS

11.1 Ethical Considerations

The study will abide by the principles of the World Medical Association Declaration of Helsinki (1996), the principles of GCP and in accordance with all applicable regulatory requirements, including but not limited to the Research Governance Framework and the Medicines for Human Use (Clinical Trial) Regulations 2004, as amended in 2006 and any subsequent amendments.

This protocol and related documents will be submitted for review to the REC, and to the MHRA for Clinical Trial Authorisation.

The Chief Investigator will submit a final report at conclusion of the trial to the KHP-CTO (on behalf of the Sponsor), the REC and the MHRA within the timelines defined in the Regulations.

There are no major ethical issues however the following points have been considered:

- Study interventions: Whilst both CyA and MTX have potential side effects, both
 medications are used in standard NHS practice. Full information about possible risks
 and benefits of both medications will be provided to parents and participants and
 data on adverse events will be collected and monitored throughout the trial. In
 addition, the treatment of severe atopic eczema in participants will not be
 compromised by participation in the trial. The precise risks and benefits of
 participating in the study will be outlined in patient information sheets, to be
 formulated with service user involvement.
- Blood and other tests: The risks of taking blood include temporary discomfort from
 the needle in the arm, bleeding, bruising, swelling at the needle site and, in rare
 instances, infection. None of the other investigations and procedures, including BP
 measurement, urine testing, and tape stripping are uncomfortable or harmful.
- Ongoing treatment after the study has been completed: All participants will be
 able to receive further systemic immuno-suppressive therapy via the NHS if required,
 after the study has been completed.
- Consent in paediatric population: Children up to the age of 16 will be eligible for enrolment in the trial and so age-appropriate Participant Information Sheets (PISs) will be prepared in line with current guidelines. Please see section 11.2 for further details.

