11.2 Ethical Approval

The trial protocol will not be initiated until it has received the favourable opinion of a Multi-centre Research Ethics Committee (MREC). Subsequent to this, it must also undergo independent review at R&D offices at the R&D offices at participating sites. The local R&D office should be sent the appropriate site specific information form complete with the necessary authorisation signatures, plus any other documentation requested for review. A copy of local Research & Development (R&D) approval should be forwarded to CTRC before the site is initiated and patients recruited.

Children from the age of 2 to 16 will be eligible for enrolment in the trial. Proxy consent from the parent or legally acceptable representative should be obtained prior to each patient participating in the trial, after a full explanation has been given of the treatment options, including the conventional and generally accepted methods of treatment. Age and stage-of development specific Patient Information and Consent Forms (PISC) should also be implemented and patient assent obtained where appropriate. The right of the parent/ legal representative to refuse consent for the minor to participate in the trial without giving reasons must be respected. After the patient has entered the trial, the clinician must remain free to give alternative treatment to that specified in the protocol, at any stage, if he/she feels it to be in the best interest of the patient. However, the reason for doing so should be recorded and the patient will remain within the trial for the purpose of follow-up and data analysis. Similarly, the parent/legal representative of the patient remains free to withdraw the patient at any time from the protocol treatment and trial follow-up without giving reasons and without prejudicing the further treatment of the minor.

For children of school age, efforts will be made to arrange appointments outside of school hours whenever possible.

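### Section 7.7.2 prohibits systemic treatment throughout the study with no exemption after trial treatment stops, yet re-starting it is a trigger of the second co-primary endpoint and other sections allow it

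*Protocol*

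**What the plan says.** **The prohibition.** Protocol section 7.7.2 states "The following therapies are prohibited during the study" and addresses this to all patients. The list contains "Concomitant systemic anti-inflammatory or immunosuppressant medication, including but not limited to azathioprine and mycophenolate mofetil" and, as a separate item, biologic agents. Neither item carries an end date or an exemption for follow-up. Section 7.7 defines the term used: "A concomitant medication/treatment is any drug or substance administered between the screening visit and the visit at week 60". Section 8.1 gives the time frame: "Patients will receive IMP for 36 weeks and followed up for 60 weeks post randomisation". Section 11.1 says that participants will be "able to receive further systemic immuno-suppressive therapy via the NHS if required", and it speaks only of the time after the study is complete.

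**The endpoint.** Section 8.2 defines the second co-primary outcome as the earliest "time that a patient either re-started systemic treatment or returns to their baseline o-SCORAD (or worse), following cessation of trial treatment". Section 9.6 repeats both triggers. The footnote to 8.2 explains that the re-start trigger was added because many children were thought unlikely ever to return to their baseline score and yet likely to need systemic therapy.

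**Passages that expect or allow systemic treatment after cessation.** Sections 6.5.2 and 10.7 set safety reporting for ciclosporin or methotrexate given as routine care once trial treatment has stopped. Section 11.2 says that "the clinician must remain free to give alternative treatment to that specified in the protocol, at any stage", with the patient kept in follow-up and in the analysis. Section 7.7.1 permits rescue oral corticosteroids, and allows rescue medication in both the treatment and the follow-up period.

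**The concern.** For a child who completes treatment, the second co-primary endpoint is observed from week 36 to week 60. On the wording of 7.7 and 7.7.2, the prohibition covers those same 24 weeks. A site that reads 7.7.2 literally has a reason to withhold or delay systemic treatment until week 60, and one of the two triggers then rarely fires there. A site that works from 8.2 or 11.2 re-starts treatment when the clinician sees the need, and records events.

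The trial is open-label for the local team (section 6.4.2). The o-SCORAD trigger rests on a blinded assessor, but the decision to re-start lies with a clinician who knows the allocation. One reading applied everywhere would delay or remove events in both arms. Readings that differ by site add variation unrelated to the drugs, and a reading applied differently by arm would bias the comparison. Unclear rules on when re-start is permitted are therefore a weakness in a co-primary endpoint.

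**Working it through.** **1. The passages side by side**

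| Question | 7.7, 7.7.2, 11.1 | 8.2, 9.6, 6.5.2, 10.7, 11.2 |
|---|---|---|
| Systemic treatment after trial treatment stops? | On the 7.7.2 list for the whole study; concomitant runs to week 60; 11.1 mentions further therapy only after the study | An endpoint event (8.2, 9.6); foreseen as routine care (6.5.2, 10.7); open to the clinician (11.2) |
| Exemption or cross-reference to the other side? | None | None |
| What should a site do with a re-start at, say, week 40? | 7.7.2 gives an instruction only for patients who stop study drug because of a prohibited therapy | 8.2 counts it as a flare |

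Reading concomitant as meaning alongside study drug would resolve the conflict, but the definition in 7.7 does not permit it. The log of changes for version 6.0 (section 18.5) records the refinement of the co-primary outcome and lists no change to 7.7.2. A plausible explanation is that the endpoint was revised and the prohibited list was not revisited.

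**2. The plan's own figure**

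Inputs from section 9.6: flare rates 86% and 56%, two-sided alpha 0.025, power 80%. With mean rate 0.71 and z values 2.2414 and 0.8416:

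n = [2.2414 × √(2 × 0.71 × 0.29) + 0.8416 × √(0.86 × 0.14 + 0.56 × 0.44)]² / 0.30² = (1.438 + 0.510)² / 0.09 = 42.2, so 43 per group. This is the stated figure. Power at 43 per group is 0.809.

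**3. Can the effect on power be sized?**

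Only with an assumption. Let s be the share of flares, equal in both arms, that would show only as a re-start. Suppose that all of these are suppressed and none later appears through the o-SCORAD trigger. Both rates are then multiplied by (1 − s). With 43 evaluable per group:

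| s (assumed) | Rates | Events, 43 × (p1 + p2) | Power, two proportions | Power, log-rank |
|---|---|---|---|---|
| 0 | 86% vs 56% | 61 | 0.81 | 0.88 |
| 0.10 | 77.4% vs 50.4% | 55 | 0.65 | 0.71 |
| 0.25 | 64.5% vs 42% | 46 | 0.44 | 0.47 |
| 0.50 | 43% vs 28% | 31 | 0.21 | 0.22 |

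The log-rank column uses the events formula Φ(√(events/4) × |ln HR| − 2.2414), with HR = ln(1 − p2)/ln(1 − p1). At s = 0, HR = ln 0.44 / ln 0.14 = 0.418. The log-rank test is the one planned in section 9.7, and it shows the same pattern.

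The arithmetic is sound, but the protocol gives no value for s. For any given s the table is also the worst case of this kind: treatment that is delayed but still starts before week 60 costs less, and a child left untreated may reach the o-SCORAD trigger instead. The table shows that the endpoint is sensitive to lost re-starts. It does not measure this defect.

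**The case against.** The strongest reply is that no site would read 7.7.2 as a ban on treating a flaring child who is off study drug. Several passages support that reply.

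- Section 7.7.2 itself leaves room for an on-treatment reading. Its live-vaccine item covers the time in the study and a further 12 weeks after the last dose. With a last dose at week 36 those 12 weeks end at week 48, so if the time in the study ran to week 60 the extra clause would add nothing for a child who stays in follow-up.
- The only consequence stated for the listed therapies concerns patients still on study drug.
- Section 11.1 reassures and does not prohibit; it also says that treatment of severe eczema will not be compromised by taking part.
- Sections 6.5.2, 10.7 and 11.2 plainly contemplate such treatment, and the 8.2 footnote says that the oversight committees agreed the definition.

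This makes withholding at every site unlikely. It does not remove the definition in 7.7 or the missing exemption. It shows that two readings are open to sites, which is the defect.

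A reader might go further in four ways that the documents do not support:

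- **That the protocol forbids the endpoint's main trigger.** It forbids it in one place and allows it in others. Re-start is one of two triggers, and the footnote speaks of many children without giving a share.
- **That power falls to a stated value such as 21%.** That needs an assumed share and complete suppression.
- **That re-starts will be censored or excluded as deviations.** Section 9.7 plans intention to treat on all randomised participants, section 11.2 keeps these patients in the analysis, and the protocol describes no deviation-based analysis.
- **That any systemic treatment after cessation should count as a flare.** That would sweep in the rescue oral corticosteroids that 7.7.1 permits and so widen the co-primary event.

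**Conclusion.** The contradiction is in the current text and should be resolved. Sections 7.7 and 7.7.2 taken together prohibit to week 60, without exemption, what 8.2 and 9.6 count as a co-primary event and what 6.5.2, 10.7 and 11.2 foresee or allow. Section 11.1 adds to the ambiguity but is not itself a prohibition.

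The consequence is that the occurrence and timing of events in the second co-primary endpoint can depend on local reading, in a trial where the deciding clinician knows the allocation. This rests on the wording alone. How large the effect is, and whether any site has applied the prohibition in follow-up, cannot be derived from the documents.

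A related gap is part of the same point. Oral corticosteroids are systemic and are permitted as rescue, and 8.2 does not say whether starting them after cessation is a re-start of systemic treatment.

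**What to change.** 1. Reconcile sections 7.7, 7.7.2 and 11.1 with 8.2, 9.6, 6.5.2, 10.7 and 11.2, so that one period is stated for the prohibition and it agrees with the endpoint definition. Which clinical rule applies after trial treatment stops is for the sponsor to decide.
2. State in 8.2 and 9.7 that a re-start meeting the 8.2 definition is analysed as an endpoint event on its start date, and is not treated as a protocol deviation or a reason for censoring.
3. State whether the rescue oral corticosteroids permitted in 7.7.1 count as re-started systemic treatment for the co-primary endpoint.

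The cost is a wording amendment, one analysis rule and a note to sites. No new data are needed: section 7.7 already requires concomitant medication to be recorded to week 60.

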7.7.2.1 Those randomised to ciclosporin

Ciclosporin is extensively metabolised by CYP 3A isoenzymes, in particular CYP3A4, and is a substrate of the multidrug efflux transporter P-glycoprotein. Various drugs are known to either increase or decrease plasma or whole blood concentrations of ciclosporin.

Treatment with the following concomitant medications is prohibited during the study:

- Bosentan
- Dabigatran etexilate
- Aliskiren

- Hypericum perforatum (St. John's wort)
- Tacrolimus (except for topical treatment see section 7.7.1)
- Everolimus and sirolimus
- Lercanidipine
- Treatment with a live (attenuated) vaccine

Other drugs known to interact with ciclosporin may be prescribed at the discretion of the local Investigator when considered necessary for the patient's safety and well-being. If drugs are given concomitantly, careful monitoring for drug-related adverse effects is recommended in line with clinical practice. Investigators should refer to the SmPC for further information, and the following points should be considered:

Drugs that decrease ciclosporin concentration include:

 Barbiturates (e.g. Phenobarbital), carbamazepine, oxcarbazepine, phenytoin; nafcillin, intravenous sulfadimidine, probucol, orlistat, ticlopidine, sulfinpyrazone, terbinafine, rifampicin, octerotide.

Drugs that may increase ciclosporin concentration include:

- Nicardipine, metoclopramide, oral contraceptives, methylprednisolone (high dose), allopurinol, cholic acid and derivatives, protease inhibitors, imatinib, colchicine, nefazodone.
- Macrolide antibiotics: azithromycin, clarithromycin,
- Erythromycin (Note: Erythromycin may be used as rescue medicine but it should not be used for longer than two weeks in the trial).
- Azole antibiotics: Ketoconazole, fluconazole, itraconazole and voriconazole
- Verapamil
- Telaprevir
- Amiodarone
- Danazol
- Diliazem
- Imatinib

Care should also be taken when using ciclosporin together with other active substances that exhibit nephrotoxic synergy such as: aminoglycosides (including gentamycin, tobramycin), amphotericin B, ciprofloxacin, vancomycin, trimethoprim (+ sulfamethoxazole); fibric acid derivatives (e.g. bezafibrate, fenofibrate); NSAIDs (including diclofenac, naproxen, sulindac); melphalan histamine H₂-receptor antagonists (e.g. cimetidine, ranitidine); methotrexate.

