Ciclosporin is also an inhibitor of CYP3A4, the multidrug efflux transporter P-glycoprotein and organic anion transporter proteins (OATP) and may increase plasma levels of co-medications that are substrates of this enzyme and/or transporters. Ciclosporin may reduce the clearance of digoxin, *colchicine, statins, etoposide* prednisolone, non-steroidal anti-inflammatory drugs (NSAIDs), and others.

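### The protocol's advice to avoid over-the-counter ibuprofen covers only the methotrexate arm, although it names NSAIDs as a renal hazard with ciclosporin

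*Protocol*

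**What the plan says.** Four parts of the concomitant-medication rules bear on this.

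- **Section 7.7.2**, family advice: "Patients are advised to avoid self-medication with over the counter ibuprofen if on the" methotrexate arm, because of an interaction between the two drugs. Paracetamol is the recommended alternative. Accidental use does not lead to withdrawal, and clinicians are asked to monitor closely after it. The section also says that patients and caregivers, in either arm, should be told to "notify the study site about any new medications he/she takes after the start of the study drug".
- **Section 7.7.2.1**, ciclosporin: "Care should also be taken when using ciclosporin together with other active substances that exhibit nephrotoxic synergy such as" a list of drugs that includes "NSAIDs (including diclofenac, naproxen, sulindac"). It later names "non-steroidal anti-inflammatory drugs (NSAIDs), and others" among the drugs whose clearance ciclosporin may reduce. For interacting drugs in general, "If drugs are given concomitantly, careful monitoring for drug-related adverse effects is recommended in line with clinical practice".
- **Section 7.7.1**, both arms: the permitted drugs include "Medications such as paracetamol and non-steroidal anti-inflammatory drugs (eg" ibuprofen), at "the discretion of the local PI and provided that the medication in question has no" noticeable effect on the study.
- **Section 2.4.1** gives raised blood pressure due to nephrotoxicity as the main potential side effect of ciclosporin.

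**The concern.** The protocol names a drug class, an interaction and an organ at risk for ciclosporin, but directs its family-level warning about the shop-bought member of that class only at the other arm. Ibuprofen is available without a prescription, so self-medication is the route that prescriber cautions reach least well. At stake is avoidable NSAID exposure in children taking a drug whose main stated risk comes from the kidney, in a trial where section 2.4 says both drugs are off label and calls patient safety a key secondary outcome.

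**Working it through.** No formula or planned figure is involved. The check sets the rules side by side and asks whether anything else in the protocol supplies the missing advice.

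**1. Is ibuprofen inside the ciclosporin warning?** Section 7.7.2.1 names the class and gives three examples, none of them ibuprofen. Section 7.7.1 gives ibuprofen as its example of an NSAID. On the protocol's own terms the class warning covers it.

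**2. Do the arms differ in other safeguards in a way that would explain the difference in advice?**

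| Safeguard | Ciclosporin | Methotrexate |
|---|---|---|
| Local investigator discretion over NSAIDs (7.7.1) | yes | yes |
| Interacting drugs prescribed at discretion, with monitoring (7.7.2.1, 7.7.2.2) | yes | yes |
| Site told of new medicines (7.7.2) | yes | yes |
| Action if eGFR falls by 20% or more (Tables 5 and 8) | yes | yes |
| Families advised to avoid over-the-counter ibuprofen (7.7.2) | **no** | **yes** |

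Only the last row differs. The dosing tables do not fill the gap: neither Table 4 nor Table 7 mentions ibuprofen.

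**3. Does the general ban close it?** Section 7.7.2 prohibits concomitant systemic anti-inflammatory medication in all patients. Section 7.7.1 permits NSAIDs by name, so the ban cannot be read as excluding ibuprofen.

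**4. Would monitoring make up for it?** Section 8.3 schedules on-treatment safety bloods for both arms at weeks 2, 4, 8, 12, 20, 28 and 36. The gaps are 4 − 2 = 2, 8 − 4 = 4, 12 − 8 = 4, 20 − 12 = 8, 28 − 20 = 8 and 36 − 28 = 8 weeks. Section 8.1 allows ±2 weeks per visit after week 4, so two successive visits scheduled 8 weeks apart can lie up to 8 + 2 + 2 = 12 weeks apart. Unscheduled bloods are possible in between (section 8.1.2). Bloods detect harm; they do not prevent exposure.

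**5. How many children lack the advice?** 102 randomised 1:1 gives 102 / 2 = 51 in the ciclosporin arm (section 9.6). This is the size of the arm, not the number who would take an NSAID. The protocol gives no rate of NSAID use and no NSAID-related renal risk, so expected harm cannot be calculated.

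**The case against.** The strongest reply is that this is an omission and not a contradiction. Nothing tells ciclosporin families that they may self-medicate. NSAIDs are allowed only at the local investigator's discretion, and for ciclosporin that discretion is exercised under an explicit class warning. Section 7.7.2.2, by contrast, names neither NSAIDs nor ibuprofen and refers only to salicylates and acidic anti-inflammatory agents, so the 7.7.2 bullet could be seen as methotrexate's equivalent of the ciclosporin warning. Section 2.4.1 also reports no clinically significant change in mean creatinine or blood pressure over 12 months in 42 children given ciclosporin 5 mg/kg/day, and the trial adds cystatin C and urinary NAG measurements beyond standard care. Finally, what families are actually told depends on leaflets that are not shown.

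Part of this stands. Both arms carry some NSAID precaution, renal monitoring is good, and the protocol alone cannot establish what families hear. But the two precautions address different people. One tells a family beforehand which analgesic to avoid; the other asks a prescriber to take care, and self-medication involves no prescriber. Notification concerns drugs the child takes, so it may come after exposure. The protocol gives no reason why discretion and monitoring suffice for ciclosporin when it added family advice on top of them for methotrexate. The 42-child result concerns ciclosporin in general and, as reported in the protocol, says nothing about ciclosporin combined with an NSAID.

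**Conclusion.** The point holds as a minor inconsistency in safety wording. The protocol restricts its over-the-counter ibuprofen advice to methotrexate while stating a renal interaction between NSAIDs and ciclosporin, and no other provision gives ciclosporin families equivalent advice. The gap is confined to advice on self-medication.

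Its clinical size is not estimable. No bias in any endpoint is claimed: the eGFR rule is the same in both arms and section 7.7 requires all concomitant drugs to be recorded. Sample size, power and significance level are untouched. The conclusion rests on the protocol text alone. If the ciclosporin leaflet already gives the advice, the practical risk is smaller and what remains is to bring the protocol into line with it.

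**What to change.** Reword the section 7.7.2 bullet to apply to both arms and to over-the-counter NSAIDs generally: families should avoid self-medication with them and use paracetamol; accidental use does not lead to withdrawal; and the clinician monitors closely afterwards, including renal function in the ciclosporin arm. Cross-refer to this bullet from the NSAID item in section 7.7.1 so that the permission and the precaution are read together. Check that the patient material for both arms says the same. A matching line in Table 4 is optional.

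The cost is one sentence, one cross-reference and a document check, with no new data collection. The one downside is that ciclosporin families lose a shop-bought analgesic option; paracetamol remains available.
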